### 11.6.2. Analysis of Time to Symptom Response by Symptom Relief Medication Use for Placebo-Treated Subjects

Repeat the primary efficacy analysis for the ITTI and ITT populations comparing placebo-treated subjects who did not use symptom relief medication to placebo-treated subjects who did use symptom relief medication. Sum of baseline FLU-PRO symptom assessments (<42 or  $\geq$ 42) will be included as a factor in the analysis. Pre-enrollment symptom relief medication use will not be used as a factor in the analysis since the groups being compared are classified by symptom relief medication use.

Analysis Population(s): ITTI placebo-treated subjects, ITT placebo-treated subjects

Derived Variables: See Section 11.2: Primary Efficacy Analysis

**11.6.3. Analysis of Time to Ability to Perform All Normal Activities by Symptom Relief Medication Use for Placebo-Treated Subjects**

Repeat the analysis of time to ability to perform all normal activities for the ITTI and ITT populations comparing placebo-treated subjects who did not use symptom relief medication to placebo-treated subjects who did use symptom relief medication. Sum of baseline FLU-PRO symptom assessments ( $<42$  or  $\geq 42$ ) will be included as a factor in the analysis. Pre-enrollment symptom relief medication use will not be used as a factor in the analysis since the groups being compared are classified by symptom relief medication use.

Analysis Population(s): ITTI placebo-treated subjects, ITT placebo-treated subjects

Derived Variables: See Section 11.4.1 Time to Ability to Perform All Normal Activities

**11.6.4. Proportion of Subjects Experiencing Complications of Colds by Symptom Relief Medication Use for Placebo-Treated Subjects**

Repeat the analysis of proportion of subjects experiencing complications of colds for the ITTI and ITT populations comparing placebo-treated subjects who did not use symptom relief medication to placebo-treated subjects who did use symptom relief medication using a Fisher's exact test.

Analysis Population(s): ITTI placebo-treated subjects, ITT placebo-treated subjects

Derived Variables: None

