#### 10.1.5. Prior and Concomitant Medication

The prior and concomitant medication tables will summarize the number and percentage of subjects receiving each medication by Level 4 Anatomical Therapeutic Chemical (ATC) classification and standardized medical name.

Analysis Population(s): ITT, ITTI

Derived Variables: Prior medication classification = medications with stop dates prior to screening date

Concomitant medication classification = medications with administration occurring on or after the date of the first administration of study drug until the end of the study

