## 11. EFFICACY

### 11.1. General

Unless otherwise specified, all statistical tests will use two-sided tests at the  $\alpha=0.05$  level.

The following definitions will apply to multiple efficacy analyses:

Daily Diary Period	Each daily diary period will begin 24 hours prior to the time of diary assessment and end at the time of diary assessment.
Symptom Relief Medication	Any medication taken for a symptom of colds as indicated by the subject during the study period.

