#### Definitions:

Symptom Response	The set of criteria to be defined based upon a blinded review of symptom scores (pooled for all ITTI subjects without regard to treatment group assignment) that correlate to the time at which subjects report that they return to usual health (a daily global assessment question). Methodology to be used for the derivation of the Symptom Response definition is described in Section 11.2.1 below. Symptom scores must be maintained at the defined level for at least 2 daily diary periods without any symptom relief medication during or between those 2 daily diary periods.
Time of Symptom Response	The start of the first daily diary period in which Symptom Response is achieved and is maintained for at least two daily diary periods without any symptom relief medication during or between those two daily diary periods.
Time to Symptom Response	Time (hours) from the first dose of study medication to the Time of Symptom Response.

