**Table 6: Variables Used for the Primary Efficacy Analysis**

Variable	Source	Format/Notes
Date and time of first medication intake	CRF	

Variable	Source	Format/Notes
Date and time of completion for each symptom assessment record	Subject diary	
Symptom score assessment for each symptom for each diary record	Subject diary	
The ordinal symptom severity, intensity or frequency score assessment for each of the 32 symptoms will be coded to numerical values 0-4.
 
It will not be possible for any individual symptom assessment to be missing within a diary record, therefore no individual item imputation will be required.
 
In the event that the diary was not completed at a specified time point (e.g., Day 2), the missing data will not be imputed.

Date and time of symptom relief medication intake	Sponsor-provided listing	The list of symptom relief medications will be selected from the listing of all concomitant medications prior to unblinding.

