#### **11.2.2. Analysis of the Primary Efficacy Parameter**

The primary efficacy parameter, time to Symptom Response, will be derived as follows:

Event: Time of Symptom Response – time of the first dose

Censored: Time of last symptom assessment – time of the first dose

If Symptom Response is achieved at the time of the first symptom assessment diary record, the subject will be excluded from the analysis.

If Symptom Response is not achieved prior to a subject’s last available diary assessment, but the criteria are met at the last available diary assessment with no evidence of symptom relief medication intake during that diary period, time of Symptom Response will be considered to have occurred at the start of the last daily diary period.

Time to Symptom Response for the NTZ treatment group will be compared to that of the placebo treatment group using a Gehan-Wilcoxon test stratified by (1) time from onset of illness to time of first dose of study medication (0-24, >24-≤36, or >36 hours from onset), (2) pre-enrollment use of symptom relief medication, and (3) presence of underlying lung condition including asthma, COPD, or past or present history of smoking. The comparison will be graphically depicted using Kaplan-Meier curves.

Analysis Population(s): ITTI

Derived Variables: Event: Time of Symptom Response – time of first dose

Censored: Time of last symptom assessment – time of first dose

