#### 11.4.1. Time to Ability to Perform All Normal Activities

Definitions:

Ability to Perform All  
Normal Activities

Subject reports a score of 10 on the 0-10 scale for ability to perform normal activities and maintains the score for at least two consecutive daily diary periods without symptom relief medication during or between those two daily diary periods

Time of Ability to Perform

All Normal Activities	The time of the first daily diary entry in which the subject achieves Ability to Perform All Normal Activities
Time to Ability to Perform All Normal Activities	Time (hours) from first dose to the Time of Ability to Perform All Normal Activities

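### SAP 11.6.2–11.6.3 compare placebo users and non-users of symptom relief medication without a time window; on the natural reading, longer illness itself makes a subject a user, so users look slower even if the medication does nothing

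*SAP*

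**What the plan says.** SAP 11.6.2 repeats the primary analysis in placebo subjects of the ITTI and ITT populations, "comparing placebo-treated subjects who did not use symptom relief medication to placebo-treated subjects who did use symptom relief medication". SAP 11.6.3 does the same for Time to Ability to Perform All Normal Activities. Both add the baseline FLU-PRO sum, cut at 42, as a factor. SAP 11.6.2 also says "Pre-enrollment symptom relief medication use will not be used as a factor in the analysis", on the ground that the groups are themselves formed by symptom relief use.

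Neither subsection defines a user or a window. Their derived-variable lines point back to SAP 11.2 and 11.4.1, which contain no such variable. The nearest guidance is elsewhere:

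- SAP 11.1 defines symptom relief medication, for several efficacy analyses, as "Any medication taken for a symptom of colds as indicated by the subject during the study period".
- SAP Table 6 says "The list of symptom relief medications will be selected from the listing of all concomitant medications prior to unblinding".
- SAP 10.1.5 defines concomitant medications as "medications with administration occurring on or after the date of the first administration of study drug until the end of the study".

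Both endpoints carry a medication-free condition. For Symptom Response (SAP 11.2, Definitions): "Symptom scores must be maintained at the defined level for at least 2 daily diary periods without any symptom relief medication during or between" the two periods. For normal activities (SAP 11.4.1), the subject "maintains the score for at least two consecutive daily diary periods without symptom relief medication during or between those two daily diary periods".

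SAP 3 and 8.1 give the purpose as evaluating the *impact* of symptom relief medication. Protocol 9.6 permits acetaminophen and dextromethorphan when symptoms are disabling and states no day limit.

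**The concern.** Read together, SAP 11.1, Table 6 and 10.1.5 make *did use* mean any use between first dose and end of study. Group membership is then decided after time zero and depends partly on the outcome: a subject who recovers on Day 3 has two or three ill days in which to become a user, and one who is ill for 20 days has about 20. Slow recovery creates users. A severity score measured at baseline cannot correct for time at risk of exposure that accrues afterwards.

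The medication-free condition pushes the same way, though less strongly: a dose taken in a period that already meets the symptom or activity criterion postpones the event for a user and never for a non-user.

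The stated question is one of impact. Protocol 1.1.1 reports longer illness in subjects of earlier antiviral trials who had used relief medication before enrollment, and says it is unclear whether severity or the medication was responsible. The planned comparison could return users slower when neither explanation is true, and could be read as evidence that common symptom relief medicines prolong colds.

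**Working it through.** **Plan figures.** The plan states no figure for these analyses. Its sample size supplies the group size: 600 × 0.88 = 528, about the 530 complete subjects in Protocol 8.1, with 300 per arm. So n = 300 placebo ITTI subjects.

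**Mechanism.** If the chance of a dose on each ill day is p, the chance of becoming a user over d ill days is 1 − (1 − p)^d. At p = 0.05 this is 1 − 0.95³ = 14% for 3 ill days and 1 − 0.95²⁰ = 64% for 20.

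**Recovery curve.** Protocol 8.1 and SAP 8.3 base placebo recovery on time to normal activities in RM08-3002. Protocol Table 7 gives placebo quartiles of 135, 302 and 643 h. A two-piece lognormal through all three has σ = ln(302/135)/0.6745 = 1.19 below the median and ln(643/302)/0.6745 = 1.12 above it. Recovered by 48 h: Φ(ln(48/302)/1.19) = 6.2%. Not recovered by 504 h: 1 − Φ(ln(504/302)/1.12) = 32%. A single lognormal (138/302/661 h) served as a check.

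**Null simulation.** Medication has no effect on recovery. Doses are possible only on ill days, equally likely whatever the stage of illness; censoring is at 504 h; the test is Gehan-Wilcoxon; trials with z < −1.96 are counted (nominal 2.5%). The use patterns are assumptions. Ranges span the two curves and repeat runs.

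| Assumed use while ill | Users falsely slower, ever/never grouping |
|---|---|
| 30% per day, Days 1–2 only | 3–5% |
| 40% on Day 1, halving daily | 10–11% |
| 30% per day, Days 1–3 | 14–17% |
| 60% on Day 1, halving every two days | 60–63% |
| 20% per day, Days 1–5 | 60–64% |
| 2% on every ill day | over 99% |

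Spurious medians, users against non-users: 321 and 295 h (Days 1–3), 338 and 262 h (Days 1–5), 493 and 196 h (5% per ill day).

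**First-record rule.** SAP 11.2.2 says "If Symptom Response is achieved at the time of the first symptom assessment diary record, the subject will be excluded from the analysis". The table drops subjects recovered by 24 h. If the first record is instead the baseline diary (Protocol 5.2), they stay in, and the two-piece curve gives 8%, 26% and 75% for Days 1–2, 1–3 and 1–5.

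**Other recovery curves.** Matching the Protocol Table 5 placebo quartiles gives 4%, 18% and 85% for Days 1–2, 1–3 and 1–5. Separate Weibull fits to the first quartile and median of each table give 8–10% for Days 1–2 use and 97.5–100% for 3–20% use per ill day.

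**Control and direction.** In the Weibull runs, use unrelated to symptoms over a fixed 21 days, with no medication-free rule, gives 2.3–3.0%, so the link between use and being ill is the cause. If use is more frequent after recovery than before, the bias reverses (hazard ratio 1.26–1.65). That conflicts with medication taken for a cold symptom, but it marks the limit of the directional claim.

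**Baseline score.** Stratifying by a two-level score (assumed correlation 0.4 with log duration) leaves 15% for Days 1–3 and 57% for Days 1–5.

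**Medication-free rule alone**, with exposure fixed in advance: 3–5% if users dose on 5–10% of days that already meet the criterion, and 9–10% at 20%.

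**48 h landmark.** False users-slower rates by what drives use:

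- Equally likely on all pre-recovery days: about 2–3%.
- Confined to the first half of each illness, five early-use patterns: 6–10%.
- Confined to the first third, same patterns: 16–32%. Ever/never was worse in every one of these cases; Days 1–2 use, for instance, rises to 64% at one third.
- Rising with severity (assumed log-odds 0.7 per SD, correlation 0.3–0.5), Days 1–3 use, score-stratified: 8–16%, against 29–45% for ever/never.

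**The case against.** **The SAP never says any on-study use.** SAP 11.1 defines which medications count, Table 6 supplies intake times for the endpoint, and 10.1.5 serves summary tables. Dropping the pre-enrollment factor as redundant with the grouping could even mean that use before the first dose forms the groups, in which case the time-related bias would be absent. This stands in part. Any on-study use is the natural reading, not a stated rule, and a reader should not infer that the SAP specifies it. On either reading the user variable is undefined.

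**The size rests on assumptions.** This stands. No use rate is given and the results span almost the whole scale. Even the small figure for Days 1–2 depends on use being equally likely throughout the illness. Only the direction is robust, and only when use is mainly symptomatic.

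**It hardly matters.** These analyses sit under Other Exploratory Analyses, outside the hierarchy in SAP 11.4. No conclusion about nitazoxanide rests on them, and the plan already adds a severity factor. This stands as to severity. It does not rescue the comparison, because following the natural reading gives a biased answer to the question the SAP poses.

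**A landmark is no cure.** This also stands: bias remains when use is confined to early illness or tracks severity.

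**Conclusion.** The point holds with low severity. SAP 11.6.2–11.6.3 leave the exposure undefined. On the natural reading the comparison is biased towards slower recovery in users when the medication has no effect, and the baseline score does not repair it. Under assumed use patterns, the Table 7 placebo curve and 300 subjects, the false users-slower rate runs from about 4% to over 99% against a nominal 2.5%. The medication-free condition adds a smaller bias in the same direction.

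Three stronger inferences are not supported:

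- That the treatment comparison is compromised. These analyses contain placebo subjects only, and the randomised test does not use this grouping.
- That the bias is necessarily large. That depends on use patterns the documents do not report.
- That SAP 11.6.4 (complications) is shown to be defective. It uses the same undefined grouping, but no bias was demonstrated there.

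**What to change.** 1. Define a user by relief medication taken up to a fixed early landmark, for example 48 h after first dose, among subjects who have not yet responded, and count time from the landmark. If later or sparse use matters, treat use as a time-dependent exposure instead.
2. State whether pre-enrollment use counts.
3. Report the result as an association rather than an impact, because confounding by severity and symptom-driven use remain.

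Applying the same landmark in SAP 11.6.4 is optional.

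**Cost.** SAP wording, one derived variable and a rerun of the planned test; a time-dependent exposure would need a model in place of that test. Intake times are already collected (Protocol 5.10). SAP 7 allows revision before database lock and requires later deviations to be noted in the study report.

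**Downside.** The landmark drops the roughly 6% who respond by 48 h and ignores later first use. It also leaves few users when use is sparse: at 2% per ill day, 300 × 0.938 × (1 − 0.98²) ≈ 11, although about 22% would use at some point. The landmark does not touch the medication-free condition, so that smaller bias should be stated as a limitation.

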Based on the Phase 2 studies, two parallel Phase 3 studies of pleconaril were designed to evaluate efficacy using time to alleviation of symptoms as a primary endpoint. Symptom alleviation was defined as rhinorrhea graded absent and the other five symptoms graded absent or mild for 48 hours without the use of symptom relief medication. Enrollment was restricted to subjects presenting to the clinic within 24 hours of symptom onset. Other important subject selection criteria included otherwise healthy subjects at least 18 years of age with moderate to severe rhinorrhea and at least one other moderate or severe respiratory symptom (nasal congestion, cough, or sore throat). Subjects were excluded if they had fever, recent history of allergic rhinitis, if they had received asthma treatment within the previous two months, or if they had chronic cough, any known immunodeficiency, or any underlying medical condition that would confound study results. Enrollment was stratified based on smoking status and pre-treatment use of symptom relief medication, and subjects were allowed to take acetaminophen or dextromethorphan as needed for symptoms. The studies were conducted from August through November 2000 and enrolled a total of 2,096 subjects including 1,363 (65%) with laboratory-confirmed picornavirus infection. Time to alleviation of symptoms was significantly shorter for the pleconaril group compared to placebo in both studies, with median treatment benefits of 0.6 days (6.6 compared to 7.2 days, P=0.037) and 1.5 days (6.2 compared to 7.7 days, P=0.001) separately and 1.0 days (6.3 compared to 7.3 days, P<0.001) in a pooled analysis. Pleconaril-treated subjects also had improvements in time to resolution of individual symptoms and time to self-assessed “no cold” status ([Hayden et al. 2003](#)). Subjects who used symptom relief medication prior to enrollment had longer times to alleviation of symptoms. It is unclear whether the symptom relief medication use was the result of more severe symptoms or if the prolonged symptoms were the result

of suppression of cytokines and resulting prolonged viral replication ([USDHHS FDA Division of Antiviral Drug Products 2003](#)).

Vapendavir

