## 8. STUDY DESCRIPTION

### 8.1. Study Objectives

The primary objective of this study is to evaluate the effect of NTZ administered orally 600 mg b.i.d. for 5 days in reducing the duration of symptoms of colds due to EV/RV infection compared to that of a placebo during 21 days of follow-up based upon the FLU-PRO® patient-reported outcome instrument.

A key secondary efficacy objective is to evaluate the effect of NTZ compared to placebo on time to return to ability to perform all normal activities.

Another secondary efficacy objective is to evaluate the effect of NTZ compared to placebo on the proportion of subjects experiencing one or more complications of colds due to EV/RV infection including pneumonia, otitis media, bronchitis, sinusitis, exacerbations of asthma or COPD, worsening of pre-existing health conditions, secondary infections requiring systemic antibiotic use, hospitalization due to cold or complications of the cold, and death due to cold or complications of the cold.

Exploratory efficacy objectives include evaluating the effect of treatment with NTZ on the time to response for each FLU-PRO symptom; time to response for each FLU-PRO domain; time to return to usual health; changes in viral titers from Baseline to each of Days 2, 3 and 7; time to symptom response for all subjects treated (ITT population); time to symptom response for subjects infected with individual non-EV/RV viruses; and time to symptom response for subjects who received the first dose of study medication 0-24, >24-≤36, or >36 hours from symptom onset. A final exploratory objective is to evaluate the impact of symptom relief medication use on time to symptom response, time to return to ability to perform all normal activities, and proportions experiencing complications of colds for placebo-treated subjects.

Other important objectives include evaluation of the safety of NTZ by analysis of adverse events and evaluation of relationships between pharmacokinetics and clinical or virologic responses.

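### SAP 11.6.2 and 11.6.3 compare placebo users and non-users of symptom relief medication on endpoints that require medication-free days, which can make users look slower when their scores are the same

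*SAP*

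**What the plan says.** SAP 8.1 gives the purpose: "A final exploratory objective is to evaluate the impact of symptom relief medication use on time to symptom response", and likewise on time to normal activities and on complications, in placebo-treated subjects.

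SAP 11.6.2 repeats the primary analysis "comparing placebo-treated subjects who did not use symptom relief medication to placebo-treated subjects who did use symptom relief medication". Its variables come unchanged from the primary analysis: "Derived Variables: See Section 11.2: Primary Efficacy Analysis". SAP 11.6.3 does the same with the key secondary endpoint of 11.4.1. Both add the baseline FLU-PRO sum (split at 42) as a factor and drop the pre-enrollment medication stratum.

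The endpoints carry a medication-free condition. Symptom Response (SAP 11.2) must hold "without any symptom relief medication during or between those 2 daily diary periods". Ability to Perform All Normal Activities (SAP 11.4.1) must hold "without symptom relief medication during or between those two daily diary periods". The rule that accepts a single qualifying last diary also requires no such medication in that period (SAP 11.2.2 and 11.4.1).

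SAP 11.1 defines symptom relief medication as "Any medication taken for a symptom of colds as indicated by the subject during the study period". Sections 11.6.2 to 11.6.4 give no time window or minimum amount of use for counting someone as a user. SAP 11.6.4 (complications) does not use the medication-free condition.

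**The concern.** In the randomized comparison the medication-free condition is a sensible way to handle rescue use. In 11.6.2 and 11.6.3 that use is the exposure under study, so the exposure sits inside the outcome.

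Suppose two placebo subjects meet every criterion from Day 6 onward. The non-user's response is dated to Day 6. The user takes a dose in the Day 6 and Day 8 periods, so the first clean pair is Days 9 and 10. The user is recorded as recovering three days later on identical scores.

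The risk is a false reading. Protocol 1.1.1 says of an earlier antiviral program: "It is unclear whether the symptom relief medication use was the result of more severe symptoms or if the prolonged symptoms were the result" of cytokine suppression and prolonged viral replication. A finding from 11.6.2 that users recover later could be cited as evidence on that question when it partly reflects how long people keep taking medication. The baseline-severity factor does not help, because the problem lies in the endpoint and not in who becomes a user.

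**Working it through.** **Inputs**
- Placebo subjects, ITTI: 530/(1 − 0.12) = 602, against the stated 600 (600 × 0.88 = 528, approximately the 530 wanted). Half is 300 (Protocol 8.1, SAP 8.3). The 90% power cannot be checked because the curves are not shown; it is not in dispute.
- Placebo subjects, ITT: at most 1,750/2 = 875 (Protocol 8.1).
- Placebo curves, median (quartiles): Table 5, alleviation of symptoms, 146.5 h (92–298); Table 7, return to normal activities, 302.0 h (135–643). Protocol 8.1 and SAP 8.3 assume that time to Symptom Response follows the normal-activities curve, which is Table 7.
- Target effect 48 h; follow-up 21 days (504 h).
- Assumption: users take medication on a share p of the days that already meet the criteria. The documents do not give p, so a range is shown.

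**Direction.** For a fixed symptom course, adding the condition leaves a non-user's event time unchanged. A user's becomes equal or later. One medicated period blocks two possible start days.

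**Mean delay.** With q = 1 − p and independent days, the expected number of days to complete the first run of two clean days is (1 − q²)/(q²(1 − q)). Without medication it is 2. The mean delay is 24 × [(1 − q²)/(q²(1 − q)) − 2] h.

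| p | Days to two clean days | Mean delay (h) | Delay/48 h |
|---|---|---|---|
| 0.06 | 0.1164/0.0530 = 2.196 | 4.7 | 9.8% |
| 0.10 | 0.19/0.081 = 2.346 | 8.3 | 17.3% |
| 0.20 | 0.36/0.128 = 2.813 | 19.5 | 40.6% |
| 0.30 | 0.51/0.147 = 3.469 | 35.3 | 73.5% |

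The last column is only a yardstick, since 48 h is a difference in medians.

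**False-positive rate.** Simulated placebo subjects, half users at random, no medication effect, 21 daily diaries, unstratified Gehan-Wilcoxon test at two-sided 5%:

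| Curve, placebo subjects | p = 10% | p = 20% | p = 30% |
|---|---|---|---|
| Table 5, 300 | 10% | 31% | 67% |
| Table 7, 300 | 9% | 10% | 19% |
| Table 7, 875 | 8% | 20% | 46% |

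Repeat runs on Table 7 with 300 subjects gave 3% to 9% at p = 10% and 18% to 25% at p = 30%. At p = 10% the inflation is therefore small and not clearly separable from simulation error.

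**Other patterns of use** (300 subjects; underlying median 302 h, or 168 h as an assumption). The figures are the share of trials with users significantly slower, nominal 2.5%:
- No medication on qualifying days: 2–3%.
- Use continuing 1, 2 or 3 days past the point where the criteria are met: 7–25%, 24–86% and 54–100%.
- Condition removed: 1–4% throughout.
- Medication truly shortens symptoms by 15% but continues 2 days past that point: adding the condition lowers significant findings of faster recovery in users from 17% to 1% (302 h) or from 29% to 0% (168 h). In the 168 h case, significantly slower findings rise from 0% to 41%.

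**A second bias.** If anyone who ever takes medication during follow-up is a user, and the daily chance of use is 5–10% while ill and zero afterward, users are significantly slower in 100% of null trials even without the condition. The spurious median difference is about 5 to 13 days. Longer illness simply gives more days on which to become a user.

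**The case against.** Four points have force.

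1. *Medication taken while ill costs nothing.* The condition matters only on days that already qualify, or on the neighboring day of the pair. Protocol 9.6 limits the permitted acetaminophen and dextromethorphan to disabling symptoms, which argues for little use once all 32 items are at their thresholds. The argument is weaker for an activity score of 10, and SAP 11.1 counts any medication taken for a cold symptom. The exclusion of first-diary responders (SAP 11.2.2) can also offset the bias slightly.
2. *Table 5 is not the plan's assumed curve.* A reader might take the Table 5 rates as the size of the problem. On Table 7, recovery is later and more spread out, and the inflation is much smaller.
3. *The exposure is not fully settled.* Pre-enrollment use is dropped as a factor because the groups are classified by medication use, which could be read as grouping on pre-enrollment use. The link with the endpoint would then be only indirect. The Protocol 1.1.1 remark also concerns use before enrollment, so it does not show that the on-study question was the open one.
4. *Removing the condition is not a complete remedy.* Ever-use grouping remains biased. Medicated days may show drug-lowered scores, and the thresholds in SAP 11.2.1 are calibrated on medication-free return to usual health.

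All four limit the size of the bias or shape the fix. None removes the structural point: with on-study use as the exposure, the condition acts in one direction only, and the SAP gives no version of either endpoint without it.

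**Conclusion.** The point holds in conditional form. As specified, 11.6.2 and 11.6.3 cannot separate continued illness from continued medication, and they can show users as slower when symptom and activity scores follow the same course.

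A reader might infer that users must come out slower. The documents do not support that. Only the direction of the condition's effect is fixed; its size depends on unreported use on qualifying days, and it is nil if use stops once the criteria are met. On the plan's assumed curve the false-positive rate ranges from near nominal at 10% of such days to about 19% (300 subjects) or 46% (875 subjects, the maximum ITT size) at 30%. These figures assume random user status, half the subjects being users, and no true effect.

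Nor does the point reach the randomized results. These are exploratory, placebo-only analyses outside the testing hierarchy of SAP 11.4, and 11.6.4 does not use the condition. Priority is low.

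**What to change.** In SAP 11.6.2 and 11.6.3 only:

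1. Score Symptom Response as all items at or below their maximum response values on two consecutive diaries, and Ability to Perform All Normal Activities as a score of 10 on two consecutive diaries, regardless of symptom relief medication. Apply the same to the last-diary rule. The planned version can be shown alongside.
2. State how users are classified: by use up to a fixed early time (pre-enrollment use, or a landmark with follow-up counted from it), or as a time-dependent exposure. Do not group by any use during follow-up.

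Keep the medication-free condition for the randomized comparisons.

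The cost is a few sentences per section, one extra derived variable per endpoint and an exposure definition, all from data already collected. The downsides are that scores on medicated days may be lowered by the medication, the endpoints no longer match the primary and key secondary definitions exactly, and a landmark drops subjects who respond before it. SAP section 7 requires the SAP to be final before database lock. After that, the change would be a deviation noted in the study report.
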